Agriculture Home Visit Survey	2	X	
Focus Groups (Select Participants Only)	1	X	
Interviews (Select Leaders and WK Staff)	1	X	
			
			
Standard of Care Procedures	Number of Samples/Procedures	Responsible Party	
		Study	3 rd Party Payer or Participant
Basic health history and demographics	1	X	
Child weight and length/height	4	X	
WHO IYCF indicators	4	X	
MDD-W indicator	4	X	
Food Insecurity Experience Scale	4	X	
			
			
			

There will be no direct costs to subjects for participation in the study. All services provided by MHA are given for free, including the standard of care nutrition and agricultural services that are under study in this protocol. Educational and intervention components will be conducted either in the subjects' home or in a nearby community facility and, therefore, no travel costs will be incurred.

23. Compensation

Subjects will not receive any monetary compensation for participation.

24. Compensation for Research-Related Injury

N/A - This research does not involve more than minimal risk to subjects.

25. Consent Process

Consent will be obtained by the study nurse, who is trained in human subject's research ethics and a native speaker of Kaqchikel, the language spoken by most of the potential research subjects. If the potential participant agrees to take part in the study, the nurse will explain the consent process, obtain at least one caregiver's signature (or equivalent, see below for more explanation), and will enroll them in the study. The consent process will take place in participant's homes.

Subjects will not be required to provide immediate consent upon hearing about the study. The study nurse will be instructed to provide each subject with a waiting period of up to 14 days if requested before obtaining consent.

A small number of program participants, community leaders and Wuqu' Kawoq staff will be approached to participate in focus groups and community interviews, respectively, once the

PROTOCOL TITLE:

Evaluating a family-based nutrition and garden intervention in rural Guatemala

study is already underway. For these groups, a verbal consent script will be read to the participants (Appendix C) allowing them to either accept or decline to participate.

Written consent will be obtained using the attached consent form (Appendix A). Consent will be obtained by a trained study nurse who has completed relevant human subjects ethics training and who is fluent in Spanish and Kaqchikel. Many of the anticipated participants will not be literate, and so the consent form will, in most cases, be read out loud to them by the study staff. A “teach back” process will be used to assess participant understanding of the consent form content.

If participants are unable to sign their name, the study nurse administering consent will sign the form documenting that consent was administered and note that the participant is unable to sign his/her name. This process will be witnessed and attested by a independent member of the study team. The potential participant will not be required to sign with an “X” or to place a thumbprint given the political context of this region of Guatemala. During the civil war, individuals who were not literate could be made to sign documents as an oppressive strategy for extracting land titles. Hence, this study will not perpetuate those practices.

The consent form and process will make it clear that consent to participate in the research will not in any way impact the quality or quantity of clinical services, including ongoing MHA primary care and nutrition services.

An attempt will be made to obtain consent from both guardians of the child. However, consent from one parent/guardian will be sufficient for enrollment in the trial, as this study involves no more than minimal risk. Children in the study are aged 6-24 months; therefore, they are not capable of providing assent.

Informed consent documents will be in Spanish. This is because Mayan languages are largely oral languages, and no subjects in the target area can reasonably be expected to read them. Similarly, very few professionals, such as the available pool of study staff, can read them. We will conduct extensive practice sessions with the nurse leading informed consent to ensure that her ongoing oral script accurately represents the Spanish written text, in the (highly likely) case of many caregivers being unable to read the text.

26. Documentation of Consent

Written informed consent will be obtained by a research study nurse. For more details on the consent process see **Section 20. Recruitment Methods and Section 25. Consent Process**. Briefly, subjects will be approached in their home and informed consent will be obtained at that time.

Many of the anticipated participants will not be literate, and so the consent form will, in most cases, be read out loud to them by the study staff. If participants are unable to sign their name, the study nurse administering consent will sign the form documenting that consent was administered and note that the participant is unable to sign his/her name. This process will be witnessed and attested by a independent member of the study team. The potential participant will not be required to sign with an “X” or to place a thumbprint given the political context of this region of Guatemala. During the civil war, individuals who were not literate could be made to sign documents as an oppressive strategy for extracting land titles. Hence, this study will not perpetuate those practices.

PROTOCOL TITLE:

Evaluating a family-based nutrition and garden intervention in rural Guatemala

27. Study Test Results/Incidental Findings

Community health workers typically verbally share child growth results and progress and provide feedback on dietary diversity with caregivers as part of standard-of-care/child nutrition services; this will continue during the study.

Any incidental findings noted during the course of the study will be evaluated by MHA primary care medical team.

28. Sharing Study Progress or Results with Subjects

Local meetings will be held every 6-months to update each community about the study and progress. Additionally, the final study findings (in aggregate) will be shared with each community.

29. Inclusion of Vulnerable Populations

The population is highly vulnerable to coercion because of the potential for perceiving participation in the study to be a prerequisite to receiving services from MHA. The informed consent document and process will explain clearly that all families will receive the standard of care nutrition services and primary care services, whether they participate in the study or not.

There will be complete separation between nutrition services and agricultural intervention staff (community health workers, agronomist) and study research nurses. This is important, so the standard nutrition services can be delivered regardless of subjects' participation in the study.

No monetary compensation will be provided for research participation, to avoid coercive economic influence to participate.

Also, the majority of subjects will be Kaqchikel speakers with limited Spanish fluency. The study staff will be native speakers of to mitigate any language barriers. Teach back methods will be used to assess comprehension during the consent process.

Pregnant caregivers may participate in the study. The Pregnant Women Checklist has been completed below. Children 6-24 months will participate in the study. The Children Checklist has been completed below.

30. Community-Based Participatory Research

N/A- this study is not designed as CBPR. Clinical and programmatic leadership at MHA have close working relationships with local community authorities in all study communities. Local community authorities have been apprised of the planned work.

31. Research Involving American Indian/Native Populations

N/A This study does not involve American Indian/Native populations.

32. Transnational Research

PROTOCOL TITLE:

Evaluating a family-based nutrition and garden intervention in rural Guatemala

Note that this project was developed by the Guatemala team, and will be reviewed and locally overseen by the MHA IRB. The Dietetics Practice-Based Research Network ([name]) will collaborate with the study team to provide technical assistance related to study design and implementation and data analysis and interpretation.

This study will be conducted in prioritized communities of San Andrés Semetabaj, Sololá and North Tecpán, Chimaltenango. These sites were selected because they are currently being served by MHA's primary care and nutrition services. MHA has been working in this area for several years, with a focus on providing culturally and linguistically appropriate care to the Mayan indigenous population. MHA has conducted several community-based research studies in the area, and their experience informed the development of this protocol. One significant difference with U.S. culture, noted in **Section 25. Consent Process**, is that there is historical trauma associated with asking non-literate individuals to sign with an "X" or thumbprint. We have taken this into account when designing the consent process.

[name] has extensive experience with conducting cross-cultural research, with previous experience collaborating with teams from Southeast Asia and East and West Africa. She is proficient in Spanish. The research team from Guatemala has extensive experience working in the study area (providing medical care and conducting research) and are fluent in Spanish (spoken and written) and Kaqchikel (spoken – primarily an oral language). All research team members from Guatemala involved in consent and research procedures will complete human research ethics training.

The consent process has been described above in **Section 25. Consent Process** and **Section 26. Documentation of Consent**.

Clinical and programmatic leadership at MHA have close working relationships with local community authorities in all study communities. Local community authorities have been apprised of the planned work. Local meetings will be held every 6-months to update each community about the study and progress. Additionally, the final study findings (in aggregate) will be shared with each community.

33. Drugs or Devices

N/A This research does not involve any drugs or devices.

PROTOCOL TITLE:

Evaluating a family-based nutrition and garden intervention in rural Guatemala

Checklist Section

This section contains checklists to provide information on a variety of topics that require special determinations by the IRB. Please complete all checklists relevant to your research.

I. Waivers or Alterations of Consent, Assent, and HIPAA Authorization

A. Waiver of Documentation of Consent

Complete this checklist if you intend to obtain consent verbally but will not be obtaining signatures from subjects on a consent form to document consent. Waivers of documentation of consent are commonly requested when using scripts, information sheets, or email or survey introductions to present the elements of consent instead of using a traditional consent form.

1. Are you requesting a waiver of documentation of consent for some or all subjects?

All

X Some. Explain: If participants are unable to sign their name, the study nurse administering consent will sign the form documenting that consent was administered and note that the participant is unable to sign his/her name. The potential participant will not be required to sign with an “X” or to place a thumbprint given the political context of this region of Guatemala. During the civil war, individuals who were not literate could be made to sign documents as an oppressive strategy for extracting land titles. Hence, this study will not perpetuate those practices.

Verbal consent will be obtained for focus groups.

2. Provide justification for one of the following:

a) That the only record linking the subject and the research would be the consent document and the principal risk would be potential harm resulting from a breach of confidentiality. Each subject will be asked whether the subject wants documentation linking the subject with the research, and the subject's wishes will govern.

b) That the research presents no more than minimal risk of harm to subjects and involves no procedures for which written consent is normally required outside of the research context.

This research presents no more than minimal risk of harm to the subjects. Most of the study activities and procedures are part of the

PROTOCOL TITLE:

Evaluating a family-based nutrition and garden intervention in rural Guatemala

standard-of-care nutrition services delivered by MHA, and the other activities and procedures are low risk (surveys and focus groups with adults and agricultural education) and do not require written consent outside the research context.

3. Do you intend to provide subjects with a written statement regarding the research in lieu of a traditional consent form?

Yes. Please attach a copy to your submission in Click.

X No

II. Vulnerable Populations

A. Children

Complete this checklist if the subject population will include children.

1. Select the category of research that you believe this research falls within and provide justification for any associated criteria. If there are different assessments for different groups of children or arms (e.g., placebo vs. drug), include a memo to provide an assessment for each group.

X Research not involving greater than minimal risk. (*Minimal risk means that the probability and magnitude of harm or discomfort anticipated in the research are not greater in and of themselves than those ordinarily encountered in daily life or during the performance of routine physical or psychological examinations or tests.*)

Research involving greater than minimal risk but presenting the prospect of direct benefit to the individual subjects.

Provide justification for each of the following criteria:

(1) The risk is justified by the anticipated benefit to the subjects:

(2) The relation of the anticipated benefit to the risk is at least as favorable to the subjects as that presented by available alternative approaches:

PROTOCOL TITLE:

Evaluating a family-based nutrition and garden intervention in rural Guatemala

- Research involving greater than minimal risk and no prospect of direct benefit to individual subjects, but likely to yield generalizable knowledge about the subject's disorder or condition.

Provide justification for each of the following criteria:

- (1) The risk represents a minor increase over minimal risk:
- (2) The intervention or procedure presents experiences to subjects that are reasonably commensurate with those inherent in their actual or expected medical, dental, psychological, social, or educational situations:
- (3) The intervention or procedure is likely to yield generalizable knowledge about the subjects' disorder or condition which is of vital importance for the understanding or amelioration of the subjects' disorder or condition

B. Pregnant Women and Fetuses

Complete this checklist if the subject population will include pregnant women and fetuses.

X This checklist does not need to be completed if the research is both minimal risk and is not conducted, funded, or otherwise subject to regulation by DHHS, DOD, EPA, or VA.

Provide justification for each of the following:

1. Where scientifically appropriate, preclinical studies, including studies on pregnant animals, and clinical studies, including studies on non-pregnant women, have been conducted and provide data for assessing potential risks to pregnant women and fetuses.
2. The risk to the fetus is caused solely by interventions or procedures that hold out the prospect of direct benefit for the woman or the fetus; or, if there is no such prospect of benefit, the risk to the fetus is not greater than minimal and the purpose of the research is the development of important biomedical knowledge which cannot be obtained by any other means.
3. Any risk is the least possible for achieving the objectives of the research.

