MHA has a dedicated research office located in Tecpán, close to the study communities. The office has dedicated file storage cabinets for research documents, high-velocity internet, dedicated full-disc encrypted phones and computers, statistical software (STATA), and

PROTOCOL TITLE:

Evaluating a family-based nutrition and garden intervention in rural Guatemala

online HIPAA-compliant file servers and a REDcap server. The study budget includes the purchase of a new vehicle for use by the study team. An IT technician and comptroller will provide support to the project as needed.

MHA will provide usual care for treatment of severe medical illness identified during the screening/recruitment phase.

10. Prior Approvals

The protocol is approved by the MHA IRB.

11. Multi-Site Research

N/A – this is not a multi-site study

12. Study Procedures

This study will be conducted in two different sites. These are rural, Mayan language-speaking areas where MHA has been working for several years to provide primary care and child nutrition services.

This is a quasi-experimental study with an intervention group and a non-randomly selected control (standard-of-care) group.

The *standard-of-care group* will consist of subjects recruited from Maya Health Alliance's nutrition program in prioritized communities of *North Tecpán, Chimaltenango*.

The standard-of-care child nutrition services include:

- Intake visit with research nurse to assess basic health history, demographics, WHO IYCFI, FIES and MDD-W for women
- Monthly growth monitoring
- Monthly micronutrient supplementation
- Deworming medication (every 6 months)
- Monthly home visits by community health worker (CHW) to provide individualized growth assessment to mothers
- Nutrition education classes with CHW (nutrition during pregnancy, breastfeeding, complementary feeding, chronic and acute malnutrition, hygiene and nutritious recipes)

The *intervention group* will consist of subjects recruited from MHA's nutrition program in prioritized communities of San Andrés Semetabaj, Sololá. The intervention group will receive all standard-of-care child nutrition services as described above, plus:

- Agriculture education classes with the study agronomist (home garden package, assessment of plant production, weed and pest control, water access, etc.)
- Home garden supplies including seeds and/or seedlings

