- Monthly home visits from a study agronomist to provide assistance to build a garden near the family home and on-going support throughout the study

PROTOCOL TITLE:

Evaluating a family-based nutrition and garden intervention in rural Guatemala

Study data will be independently collected by a study nurse for all enrolled subjects at 0, 6, 12 and 18 months:

- Basic health history and demographics Appendix A
- Child weight and length/height Appendix B
- Household Quick Poverty Score (QPS) Appendix C
- Food Insecurity Experience Scale (household) Appendix D
- WHO Infant and Young Child Feeding indicators (child) Appendix E
- MDD-W Indicators (caregiver) Appendix F
- Agriculture Inventory Survey (household) to measure crop diversity and crop utilization Appendix G

Note that child weight and length and WHO IYCFI are already routinely collected as part of evaluation data for the standard-of-care nutrition services.

Additional data will be collected by the study agronomist for the *intervention group only* during the first agricultural home visit and at one additional agricultural home visit approximately 4 months thereafter:

- Agricultural Home Visit Baseline Survey (Baseline Agricultural Practices; Gardening Experience and Motivation) Appendix H
- Agricultural Home Visit Follow-up Survey (Adoption of Methods; Level of Home Garden Maintenance; Hours Worked in Home Garden) Appendix I

13. Data Analysis

Descriptive statistics for each group will be calculated using Stata (StataCorp, College Station, Texas). Family poverty scores will be calculated with a validated numerical scoring system commonly used in Guatemala. Changes in primary and secondary study outcomes will be compared between study groups using the chi-square test, paired t-tests (or the non-parametric equivalent) and linear and logistic regression as appropriate.

Within the intervention group, the rate of overall adoption will be compared descriptively across various demographic groups, and changes in primary and secondary outcomes will also be compared descriptively between adopters and non-adopters. Focus groups and interviews will be coded and analyzed thematically using select constructs from the Consolidated Framework for Implementation Research (CFIR) as a framework.

This is a pilot study to determine the feasibility of a garden intervention and to generate an initial effect size estimate for future, well-controlled studies. As such no formal power analysis will be performed.

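### The agronomist who delivers the garden also collects the only listed survey that names adoption, and the plan describes no independent check of it

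*Combined protocol and SAP*

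**What the plan says.** **Delivery.** Section 12 lists, among the garden services, "Agriculture education classes with the study agronomist" and "Monthly home visits from a study agronomist to provide assistance to build a garden near the family home". Section 6 gives the garden component a length of 8 months.

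**Measurement.** For the intervention group only, the same section states "Additional data will be collected by the study agronomist", "during the first agricultural home visit and at one additional agricultural home visit approximately 4 months thereafter". The later form is the "Agricultural Home Visit Follow-up Survey (Adoption of Methods; Level of Home Garden Maintenance; Hours Worked in Home Garden" survey, which is Appendix I.

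**Other outcome data.** For health history, anthropometry, poverty score, food insecurity, diet indicators and the Agriculture Inventory Survey, Section 12 says "Study data will be independently collected by a study nurse for all enrolled subjects", at 0, 6, 12 and 18 months.

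**Use.** Section 13 describes the adoption rate across demographic groups within the intervention arm and adds that "changes in primary and secondary outcomes will also be compared descriptively between adopters and non-adopters". Section 3 makes adoption, implementation and maintenance elements of the RE-AIM evaluation, which is Aim 2.

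**Checking.** The random field audits in Section 16 are listed as covering recruitment, anthropometry, dietary diversity and exit visits. The garden survey is not on that list.

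**The concern.** One role both delivers the garden and records whether the family took it up. Two mechanisms push the record upward. The agronomist may judge the results of their own teaching generously, and a caregiver may give a courteous answer to the person who brought the seeds and comes every month. Both operate at a single time point, roughly halfway through the 8-month programme, with no second observer.

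Two results are exposed. The first is the adoption rate, a central finding in a pilot whose stated purpose is feasibility. The second is the comparison of outcome changes between adopters and non-adopters, where over-rating moves non-adopters into the adopter group. Presenting these descriptively avoids a p-value but does not remove a bias in the classification.

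**Working it through.** The plan gives no adoption figure, so there is nothing of its own to reproduce. The check has two parts: who does what, and how large the error could be.

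**Roles, from the text**

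- Classes: the study agronomist (Section 12).
- Monthly support visits: a study agronomist (Section 12). The text does not say that the person surveying a family differs from the person supporting it.
- Follow-up survey on adoption, maintenance and hours: the study agronomist, once (Section 12).
- Independent rater, repeat rating, audit or agreement statistic for that survey: none described.

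**Size, as an illustration**

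Inputs: n = 70 intervention families (Section 5). Assumed: true adoption π of 30%, 50% or 70%, and a share f of 10%, 20% or 30% of true non-adopters recorded as adopters. Also assumed: no true adopter is missed, and over-rating is unrelated to outcome.

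- Recorded adoption = π + f(1 − π), so the overstatement is f(1 − π).
- Recorded adopters are a mixture of which π / [π + f(1 − π)] are true adopters. Recorded non-adopters are all true non-adopters. The recorded contrast is therefore the true contrast times that fraction.

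| π | f | Recorded adoption | Overstatement (points) | Share of contrast kept |
|---|---|---|---|---|
| 30% | 10% | 37% | 7 | 81% |
| 30% | 20% | 44% | 14 | 68% |
| 30% | 30% | 51% | 21 | 59% |
| 50% | 10% | 55% | 5 | 91% |
| 50% | 20% | 60% | 10 | 83% |
| 50% | 30% | 65% | 15 | 77% |
| 70% | 10% | 73% | 3 | 96% |
| 70% | 20% | 76% | 6 | 92% |
| 70% | 30% | 79% | 9 | 89% |

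Example: π = 0.50, f = 0.20 gives 0.50 + 0.20 × 0.50 = 0.60, and 0.50 / 0.60 = 0.83.

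For scale, the 95% half-width of a proportion in 70 families, 1.96 × √[p(1 − p)/70], runs from about 10 points (p = 0.79) to 12 points (p = 0.51). The bias can be of the same order, and a confidence interval does not show it.

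**If over-rating follows outcome**

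Let the true contrast be Δ, and let over-rated non-adopters do better than the other non-adopters by g. Measured from the mean of all true non-adopters, the over-rated sit at (1 − f)g and the rest at −fg. Write k for the share kept. The recorded contrast is then kΔ + (1 − k)(1 − f)g + fg. It exceeds Δ when g > (1 − π)Δ. With π = 0.50, f = 0.20 and g = 0.5Δ, recorded adopters sit at 0.833Δ + 0.167 × 0.8 × 0.5Δ = 0.90Δ and recorded non-adopters at −0.10Δ. The recorded contrast then equals Δ, and any larger g inflates it.

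**The case against.** The strongest case for the plan is that an agronomist is the person best qualified to judge whether agricultural methods are in use, that the analysis is descriptive in one arm of an unpowered pilot, and that Section 3 plans other implementation sources (programme documentation and auditing, focus groups, interviews). The nurse's crop survey could also serve as a cross-check. All of this limits the consequences. It does not supply a check, because nothing in the text says that any of these sources defines or verifies adoption.

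Several stronger readings are tempting, and the documents do not support them.

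- *The agronomist's rating defines the adopter groups.* This is likely but not stated. Section 13 gives no adopter definition in the supplied text, and Appendices I and J, which hold the survey and the RE-AIM instruments, are not included. The items may be direct observation or caregiver report. In either case the deliverer records them.
- *Everything else is collected by the nurse.* It is not. Qualitative and programme data come from other sources, and Section 16 mentions dietary data obtained by the nurse or a community health worker.
- *The plan breaks its own independence rule.* Section 29 says "There will be complete separation between nutrition services and agricultural intervention staff" and the research nurses, but its stated purpose is that services do not depend on study participation. It is not a measurement standard.
- *The contrast must be diluted.* That needs the two assumptions above and can reverse.
- *The nurse should replace the agronomist.* That would lose technical judgement and the 4-month timing, and would have one person record both adoption and caregiver-reported outcomes, which invites correlated error.

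**Conclusion.** The overlap of deliverer and data collector is plain in Section 12, and no independent check of the adoption survey is described. The step from that survey to the Section 13 adopter groups is a reasonable inference rather than a statement of the plan.

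Under the assumed ranges, adoption could be overstated by 3 to 21 points (2.1 to 14.7 of 70 families). The contrast would keep 59% to 96% of its size if no true adopter is missed and over-rating is unrelated to outcome. If ratings follow how well a family appears to be doing, the contrast could be inflated, so its direction of bias is not known.

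The outcomes entering the contrast are assigned to the nurse, and the primary comparison between the two groups does not use the adoption record, so it is unaffected. This is a modest, inexpensive improvement to the implementation results and not a threat to the main comparison.

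**What to change.** 1. Keep the agronomist's follow-up survey as planned.
2. Add a short checklist of directly observable items (garden present, garden maintained, taught methods in use) to the Agriculture Inventory Survey that the study nurse already gives at 6, 12 and 18 months, for completion in intervention homes.
3. In Section 13, state the adopter definition, or point to the appendix that holds it.
4. Report the adoption rate and the adopter/non-adopter contrast by both records, with their agreement. Use the nurse visit nearest the agronomist's follow-up for adoption and later visits for maintenance. The text does not say when the first agricultural visit falls. If it is close to enrolment, the survey falls near month 4 and the nearest nurse visit is month 6.

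**Cost.** A few extra minutes at visits already scheduled and brief training of the nurse, with no new staff or visits. The nurse has less garden expertise and also collects the outcomes, so the nurse's record should be limited to what can be seen and should serve as a check rather than the sole definition of adoption.
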